## 14 Publication Authorship Requirements

Authorship for any Otsuka-sponsored publications resulting from the conduct of this trial will be based on International Committee of Medical Journal Editors (ICMJE) authorship criteria (<http://www.icmje.org/recommendations>). According to ICMJE guidelines, one may be considered an author only if the following criteria are met:

1. Substantial contributions to the conception or design of the work; or the acquisition, analysis, or interpretation of data for the work; AND
2. Drafting the work or revising it critically for important intellectual content; AND
3. Final approval of the version to be published; AND
4. Agreement to be accountable for all aspects of the work in ensuring that questions related to the accuracy or integrity of any part of the work are appropriately investigated and resolved.

All authors must meet the above criteria, and all who qualify for authorship based on the above criteria should be listed as authors.

Investigators or other trial participants who do not qualify for authorship may be acknowledged in publications resulting from the trial. By agreeing to participate in the trial, investigators or other trial participants consent to such acknowledgement in any publications resulting from its conduct.

**Appendix 4****Protocol Amendment 1**

Amendment 1 Approval Date: 31 May 2019

**PURPOSE:**

The purpose of amending Protocol 031-201-00181, issued 14 Dec 2018, was to extend the treatment period by 8 weeks for subjects randomized to aripiprazole IM depot 400 mg to include an additional dose for comparison of PK parameters over the same duration as subjects randomized to aripiprazole 2M LAI 960 mg. Additional measurements of plasma aripiprazole concentrations and AUC were added. Clarification of eligibility requirements related to current use of antipsychotic medications at screening and guidance for management of the use of these medications during the trial were also added. Minor edits were made throughout the document for clarification.

**BACKGROUND:**

Changes to Protocol 031-201-00181 were made in response to a recommendation by BfArM (Germany) for an additional dose of aripiprazole IM depot 400 mg to better align the treatment duration with aripiprazole 2M LAI 960 mg, and to compare PK parameters between aripiprazole IM depot 400 mg and aripiprazole 2M LAI 960 mg over the last 8 weeks of treatment. Additional measurements of plasma aripiprazole concentrations and AUC were also requested.

**MODIFICATIONS TO PROTOCOL:****General Revisions:**

- Added an eighth dose (Day 197) for subjects randomized to aripiprazole IM depot 400 mg.
- Added 10 days (198, 199, 201, 204, 206, 209, 211, 214, 218, and 225) for collection of PK samples following administration of the eighth dose of aripiprazole IM depot 400 mg to subjects enrolled to the robust sampling schedule.
- Added 4 days (204, 211, 218, and 225) for collection of PK samples following administration of the eighth dose of aripiprazole IM depot 400 mg to subjects enrolled to the sparse sampling schedule.

## Protocol 031-201-00181

- Added collection of an additional 4 blood samples (predose and at 4, 8, and 12 hours postdose) for PK analysis after administration of the eighth dose (Day 197) for all subjects randomized to aripiprazole IM depot 400 mg.
- Added new PK parameters for plasma aripiprazole concentrations and AUC, which included a new secondary endpoint (AUC0-28 and AUC29-56 after the fourth dose of aripiprazole 2M LAI 960 mg).
- Specified the antipsychotic, mood stabilizer, and antidepressant medications allowed at screening to determine eligibility to enroll in the trial and described eligibility requirements specific to enrollment to the robust sampling schedule.
- Added guidelines for use of mood stabilizers and antidepressants by subjects with bipolar disorder during tolerability testing, oral overlap, and the treatment period.
- Reduced the number of visits that the C-SSRS would be administered to subjects enrolled to the robust sampling schedule to align the frequency of these assessments with subjects enrolled to the sparse sampling schedule.
- Added Section 8.6 Investigational Medicinal Product Reserve Sample Requirements.

## ADDITIONAL RISK TO THE SUBJECT:

There is no additional risk to the subjects.

Protocol 031-201-00181

Amendment 2 Approval Date: 31 Jul 2019

## PURPOSE:

The purpose of amending Protocol 031-201-00181, issued 31 May 2019, was to add additional C-SSRS assessments on outpatient days. Minor administrative clarifications were also made throughout the document.

## BACKGROUND:

Changes to Protocol 031-201-00181 were made to add additional C-SSRS assessments on outpatient days to the schedule of assessments for both trial treatment arms aripiprazole IM Depot 400 mg and aripiprazole 2M LAI 960 mg sparse and robust sampling schedules. Administrative changes were also made to clarify that unscheduled C-SSRS assessments will be performed during any outpatient visits, including those that may occur within 21 days after aripiprazole 2M LAI 960 mg dosing for subjects enrolled to the robust sampling schedule, and to clarify that the trial will take place from Day -30 to Day 225/ET for both treatment arms.

## MODIFICATIONS TO PROTOCOL:

### General Revisions:

- Clarified globally that subjects enrolled to the robust sampling schedule who are randomized to aripiprazole 2M LAI 960 mg and who are not able to accommodate the scheduled stay of 21 days in the clinical unit may be permitted to have some visits as outpatients with approval from the medical monitor. In addition, for any outpatient visit, an unscheduled C-SSRS will be performed.
- Clarified that the trial will take place from Day -30 to Day 225/ET for both treatment arms in Figure 3.1-1 Trial Design Schematic.
- Added C-SSRS assessments on Days 8, 15, 22, 36, 43, 50, 176, 183, 190, 204, 211, and 218 to Table 3.7-1 Schedule of Assessments: Sparse Sampling and Table 3.7.3-2 Sparse Sampling Schedule Trial Days and Activities.
- Added C-SSRS assessments on Days 36, 43, 50, 204, 211, and 218 to Table 3.7-2 Schedule of Assessments: Robust Sampling and Table 3.7.3-3 Robust Sampling Schedule Trial Days and Activities.

Protocol 031-201-00181

**ADDITIONAL RISK TO THE SUBJECT:**

There is no additional risk to the subjects.

This page is a manifestation of an electronically captured signature

## 1 Introduction

This statistical analysis plan (SAP) describes the statistical methodology and data analysis algorithms and conventions to be applied for statistical analysis and reporting of data collected under the clinical protocol 031-201-00181. The SAP is consistent with latest version of protocol amendment 2 dated on 31 July 2019.

## 2 Trial Objectives

### 2.1 Primary Objectives

The primary objectives of this trial are

- to determine the safety and tolerability of multiple-dose administrations of aripiprazole in adult subjects with schizophrenia or bipolar I disorder;
- to establish the similarity of aripiprazole concentrations on the last day of the dosing interval following the final administration of aripiprazole into the gluteal muscle site in adult subjects with schizophrenia or bipolar I disorder;
- to establish the similarity of aripiprazole exposure over the dosing interval following the administration of aripiprazole into the gluteal muscle site in adult subjects with schizophrenia or bipolar I disorder.

### 2.2 Secondary Objectives

The secondary objectives of this trial are

- to determine the PK of aripiprazole;
- to determine aripiprazole concentrations 7 days ( $C_7$ ) and 14 days ( $C_{14}$ ) after the first dose of aripiprazole for subjects enrolled to the robust sampling schedule;
- to obtain information on the efficacy of aripiprazole over the course of 32 weeks.

## 3 Trial Design

This is a phase 1b, open-label, multiple-dose, randomized, parallel-arm, multicenter (approximately 20 trial sites) trial in adult subjects with schizophrenia or bipolar I disorder. The trial design schematic is shown in [Figure 3-1](#).

Subjects between the ages of 18 to 64 years old, inclusively, are randomized (1:1 randomization) to receive multiple doses of 2 month (2M) long-acting injectable (LAI) 960 mg (4 injections) or aripiprazole IM depot 400 mg (8 injections) over the course of 32 weeks. Aripiprazole 2M LAI 960 mg are administered at 56-day intervals and aripiprazole IM depot 400 mg are administered at 28-day intervals (+/- 2 days). A final visit occurs 56 (+/- 2) days after the last dose of aripiprazole 2M LAI 960 mg or 28 (+/- 2) days after the last dose of aripiprazole IM depot 400 mg. The randomization is

Protocol 031-201-00181

stratified by PK sampling schedules (robust sampling schedule or sparse sampling schedule) and disease type (schizophrenia or bipolar I disorder). If enrollment of the number of subjects required for the robust sampling schedule is completed, the robust sampling trial sites may enroll new subjects to the sparse sampling schedule.

The trial consists of a screening period of up to 30 days, a treatment period of 169 ( $\pm 2$ ) days, and a follow-up period of 56 ( $\pm 2$ ) days after administration of the final dose for the aripiprazole 2M LAI 960 mg treatment group, or a treatment period of 197 ( $\pm 2$ ) days, a follow-up period with 28 ( $\pm 2$ ) days after administration of the final dose for the aripiprazole IM depot 400 mg treatment group. Individual participation is approximately 255 ( $\pm 2$ ) days.

Approximately 258 subjects (129 per treatment group) are to be enrolled into the trial with the expectation that approximately 170 subjects (85 per treatment group) complete the trial. An interim analysis may be conducted to ensure adequate power of the trial. Based on the possible sample size re-estimation in the proposed interim analysis, fewer subjects may be enrolled. Up to 76 subjects (38 per treatment group) are to be enrolled to the robust sampling schedule which is expected to result in at least 50 completers (25 per treatment group). And about 182 subjects (91 per treatment arm) are to be enrolled to the sparse sampling schedule which is expected to result in at least 120 completers (60 per treatment arm). Based on the possible sample size re-estimation in the proposed interim analysis, fewer subjects may be enrolled.

Protocol 031-201-00181

[figure not shown]

Figure 3-1 Trial Design Schematic

Protocol 031-201-00181

## 4 Sample Size and Power Justification

To establish the similarity in primary PK variables, the lower bound of the 90% CI of the geometric means ratio (GMR) of  $C_{56}$  and  $AUC_{0-56}$  after the fourth dose of aripiprazole 2M LAI 960 mg to  $C_{28}$  after the eighth dose and the sum of  $AUC_{0-28}$  values after the seventh and eighth doses of aripiprazole IM depot 400 mg should be greater than 80%, respectively.

It is estimated that a total of at least 100 subjects (i.e., 50 per group) completing the trial will have at least 80% power to ensure that the lower limit of the 90% CI of the GMR of  $C_{56}$  after the fourth dose of aripiprazole 2M LAI 960 mg (test) to  $C_{28}$  after the eighth dose of aripiprazole IM depot 400 mg (reference) is greater than 0.80, assuming that the actual GMR of concentrations is 1.0 and the CV is 46%.

Among these 100 subjects, at least 30 completers enrolled to the robust sampling schedule will provide at least 80% power to ensure that the lower limit of the 90% CI of the GMR of  $AUC_{0-56}$  of aripiprazole 2M LAI 960 mg (test) to the sum of  $AUC_{0-28}$  values of aripiprazole IM depot 400 mg (reference) after the seventh and eighth doses is greater than 0.80, assuming the actual GMR of concentrations is 1.15 and the CV is 40%.

The assumption of CV used in the sample calculation is based on the PK data in the previous multiple-dose aripiprazole IM depot PK Trial 31-12-298.

Assuming a dropout rate of 34%, approximately 152 to 258 subjects are estimated to be enrolled to have 100 to 170 completers based on the proposed interim analysis.

## 5 Statistical Analysis Datasets

The datasets for analyses are defined as the following:

- Randomized sample consists of all subjects who are randomized.
- Safety sample includes all randomized subjects who receive at least 1 dose of aripiprazole injection, regardless of any protocol violation.
- Pharmacokinetics sample consists of all dosed subjects who have 1 or more evaluable aripiprazole PK parameters. For analysis of the primary PK endpoint, only the completers with available values of the primary endpoints after the last scheduled injection are included.
- Efficacy sample includes all randomized subjects who receive at least 1 dose of aripiprazole injection and have at least 1 efficacy assessment.

### 5.1 Definition of Baseline and Last Visit

Baseline is defined as the last evaluable assessment prior to aripiprazole IMP injection while last visit is defined as the last evaluable assessment upon completion or early

Protocol 031-201-00181

termination of treatment phase. Only subjects who receive at least 1 dose of investigational medical products and have assessment at both baseline and at least 1 post-baseline visit are included in the analyses of change from baseline.

## 5.2 Trial Week Windows

The actual assessment date is mapped into the trial week. The definition of trial weeks for primary PK variables are described in [Table 5.2-1](#) and the definitions of trial weeks for efficacy scales and safety scales such as Extrapyramidal Symptoms (EPS) rating scales are included in [Table 5.2-2](#) and [Table 5.2-3](#). Trial days are derived from the formula: Trial Day = Date of assessment - Date of 1st IMP injection + 1. Based on the number of trial days, subjects are mapped to the corresponding trial week. For safety and efficacy variables, only the last observation within the same mapped trial week is used for imputing data on the following trial weeks in the derived last observation carried forward (LOCF) dataset. In addition, only last observations within the same mapped weeks are reported in the summary tables by trial week.

Table 5.2-1 Time Window for Trial Weeks for Primary PK Variables C28 and C56		
Scheduled Visit (Day)	Mapped Week (Trial Week)	Week Window (Trial Day Range ± 2 days)
197	28 (28 days after the 7th injection of 400 mg Abilify Maintena)	195-199
225	32 (28 days after the 8th injection of 400 mg Abilify Maintena or 56 days after the 4 th injection of 960 mg aripiprazole 2M LAI)	223-227

Table 5.2-2 Time Window for Mapping Trial Week for Efficacy Variables		
Scheduled Visit (Day)	Mapped Week (Trial Week)	Week Window (Trial Day Range)
1	Baseline	≤1 (before first IMP)
29	4	2-43
57	8	44-85
113	16	86-141
169	24	142-183
197	28	184-211
225	32	212-239

Protocol 031-201-00181

Table 5.2-3 Time Window for Mapping Trial Week for Safety Variables		
Scheduled Visit (Day)	Mapped Week (Trial Week)	Week Window (Trial Day Range)
1	Baseline	≤1 (before first IMP)
8	1	2-11
15	2	12-18
22	3	19-25
29	4	26-43
57	8	44-71
85	12	72-99
113	16	100-127
141	20	128-155
169	24	156-183
197	28	184-211
225	32	212-239

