## **3.7 Trial Procedures**

The trial will consist of a screening period of up to 30 days and a treatment period of 169 ( $\pm 2$ ) days with a follow-up period of 56 ( $\pm 2$ ) days after administration of the final

Protocol 031-201-00181

dose for the aripiprazole 2M LAI 960 mg treatment group, or a treatment period of 197 ( $\pm 2$ ) days with a follow-up period of 28 ( $\pm 2$ ) days after administration of the final dose for the aripiprazole IM depot 400 mg treatment group. Individual participation for both treatment groups will be approximately 255 ( $\pm 2$ ) days.

Subjects will provide signed informed consent prior to performing any trial procedures. Screening procedures will be performed Day -30 to -1 to determine eligibility to participate in the trial.

Subjects who meet the inclusion criteria and do not fulfill any of the exclusion criteria will return to the trial site for check-in on Day -1 or Day 1. Predose assessments and administration of IMP will be performed on Day 1. After the predose assessments, subjects will be randomized (1:1) to receive multiple doses of either aripiprazole 2M LAI 960 mg (4 injections) or aripiprazole IM depot 400 mg (8 injections) over the course of 32 weeks. Aripiprazole 2M LAI 960 mg will be administered in 56-day ( $\pm 2$  days) intervals and aripiprazole IM depot 400 mg injections will be administered in 28-day ( $\pm 2$  days) intervals.

All visits may occur within  $\pm 2$  days of the target visit date for subjects enrolled to the sparse sampling schedule and for subjects enrolled to the robust sampling schedule after discharge from the clinical unit. All subjects must return to the clinical trial site for scheduled doses, assessments, and PK sample collections. A final visit will occur 56 ( $\pm 2$ ) days after the last dose of aripiprazole 2M LAI 960 mg or 28 ( $\pm 2$ ) days after the last dose of aripiprazole IM depot 400 mg.

Trial assessments are summarized by visit in [Table 3.7-1](#) for subjects enrolled to the sparse sampling schedule and in [Table 3.7-2](#) for subjects enrolled to the robust sampling schedule.

Protocol 031-201-00181

|   | Screening        | Check-in a | Days ± 2       |       |               |    |   |    |    |     |     |     |  |     |                   |
|---|------------------|-----------------------|----------------|-------|---------------|----|---|----|----|-----|-----|-----|--|-----|-------------------|

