## 6.2 Primary Pharmacokinetics Variables

The primary PK parameters to be estimated for aripiprazole are as follows:

- Plasma concentration of aripiprazole 56 days postdose ( $C_{56}$ ) of aripiprazole 2M LAI 960 mg after the fourth dose and plasma concentration of aripiprazole 28 days postdose ( $C_{28}$ ) of aripiprazole IM depot 400 mg after the eighth dose over the course of 32 weeks;
- $AUC_{0-56}$  for aripiprazole 2M LAI 960 mg after the fourth dose, and sum of  $AUC_{0-28}$  for aripiprazole IM depot 400 mg after the seventh dose and eighth doses over the course of 32 weeks, based on the PK data from subjects enrolled to the robust sampling schedule.

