### **7.3 Treatment Compliance**

Compliance of trial medication for aripiprazole 2M LAI 960 mg and IM depot 400 mg will be summarized for the randomized sample. Compliance is defined as receiving the aripiprazole IM depot 400 mg injection in the minimum interval of 26 days or 960 mg aripiprazole 2M LAI injection at least 54 days after the prior injection.

Protocol 031-201-00181

Compliance of trial medication of oral aripiprazole in first 2 weeks is derived from total days taking oral tablets divided by 14 days for aripiprazole IM depot 400 mg injection group or 7 days for 960 mg aripiprazole 2M LAI injection group or total days in the trial if patients withdraw from the study before day 15. Proportion of subjects reaching at least 50%, 60%, 70%, 80% and 90% compliance to oral tablets are tabulated by treatment group, disease type for subjects with PK robust sampling schedule.

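### SAP Table 5.2-1 dates the primary C56/C28 sample from the first injection, while the endpoint and the table's own row label count from the last; the effect is small and limited to off-schedule last doses or final visits

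*SAP*

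**What the plan says.** **Counting from the first injection.** SAP 5.2 uses "Trial Day = Date of assessment - Date of 1st IMP injection + 1" and maps subjects to weeks by that number. Table 5.2-1 sets the window for the Week 32 primary PK sample at Trial Days 223-227.

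**Counting from the last injection.**
- The label of that same row reads "28 days after the 8th injection of 400 mg Abilify Maintena", with the matching 56 days after the fourth injection for the 2M LAI.
- SAP 6.2 and Protocol 3.5.1.2 define the test-arm endpoint as "Plasma concentration of aripiprazole 56 days postdose" after the fourth dose, and C28 correspondingly after the eighth dose of the 400 mg depot.
- SAP 3 says that the final "visit occurs 56 (+/- 2) days after the last dose of aripiprazole 2M LAI 960 mg", or 28 ± 2 days after the last 400 mg dose. Protocol 3.1 and 3.7 say the same.

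**Calendar rule for the same visit.** Protocol 3.7 also lets visits fall within ± 2 "days of the target visit date for subjects enrolled to the sparse sampling schedule", and likewise for robust-schedule subjects after discharge. Footnote n of Table 3.7-1 and footnote m of Table 3.7-2 hold outpatient PK samples on non-dosing days to ± 2 days of the specified day. Tables 3.7.3-2 and 3.7.3-3 set the final visit at Day 225 ± 2.

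**Who enters the primary PK analysis.** SAP 5 states that "only the completers with available values of the primary endpoints after the last scheduled injection are included". Neither that rule nor SAP 10.1 refers to Table 5.2-1.

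**The concern.** The two ways of counting agree when the last dose is given on its nominal day (Day 169 or Day 197). When it is not, a Trial Day window no longer measures time since the last dose, which is what C56 and C28 mean. The table can then label as C56 a sample further than 2 days from the 56-day point. It can also leave unmapped a sample taken exactly as the row label describes.

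Only the primary PK table has this gap. The efficacy and safety windows in Tables 5.2-2 and 5.2-3 are contiguous and run to Day 239, so a Day 229 rating still maps to Week 32 while a Day 229 concentration does not.

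At stake is whether the definition of a primary endpoint holds for off-schedule subjects, and whether use of their samples is settled before the data of this open-label trial are analysed.

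**Working it through.** **1. Reproduce the plan's figures.**
- Window: 225 − 2 = 223 and 225 + 2 = 227, as in Table 5.2-1.
- C56 power (SAP 4: 50 per group, GMR 1.0, CV 46%, lower 90% confidence limit above 0.80, so one-sided 0.05). Log variance = ln(1 + 0.46²) = 0.192, SD = 0.438. Standard error = 0.438 × √(2/50) = 0.0876. Noncentrality = ln(1/0.80)/0.0876 = 0.2231/0.0876 = 2.55. Noncentral-t power = 0.812, consistent with the stated 80%.

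**2. What the table accepts.** Let the last dose fall d days from its nominal day and the sample s days from Day 225, each from −2 to +2. Time since the last dose is 56 + s − d (2M LAI) or 28 + s − d (400 mg).
- Range: 52-60 or 24-32 days.
- Of the 25 (d, s) pairs, 6 have |s − d| > 2. Four are 3 days off: (−2, +1), (−1, +2), (+1, −2), (+2, −1). Two are 4 days off: (−2, +2), (+2, −2).
- The other 19 satisfy both visit rules and are 54-58 or 26-30 days postdose.

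**3. What the table leaves unmapped.** Time the sample v days (−2 to +2) from its target after the shifted dose. It falls on Day 225 + d + v. In 6 of 25 pairs |d + v| > 2, giving Day 221, 222, 228 or 229. Example: fourth 2M LAI dose on Day 171, sample 58 days later, Day 229.

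**4. Size of the timing noise.** Assume mono-exponential decline with a half-life of 20 to 24 days, from the single-dose values in Protocol 1.3.
- 3 days: factors 2^(∓3/20) = 0.901 and 1.110, 2^(∓3/24) = 0.917 and 1.091, so about 8-11%.
- 4 days: 0.871 and 1.149 at 20 days, 0.891 and 1.122 at 24 days, so about 11-15%.
- With d and s independent and uniform on −2 to +2, each has variance (4 + 1 + 0 + 1 + 4)/5 = 2 days². The table therefore gives 2 + 2 = 4 days². A ± 2-day postdose window with uniform timing gives 2. The excess is 2 days².
- As a share of log variance: 2 × (ln 2/20)²/0.192 = 1.25%, or 2 × (ln 2/24)²/0.192 = 0.87%.
- Power with log variance × 1.0125 is 0.807, and with × 1.0087 it is 0.809, against 0.812. The loss is 0.3 to 0.5 points.

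**5. Allowance for the robust schedule.** Table 3.7.3-3 heads the robust last-dose visits (Day 169, and Day 197 for 400 mg) as inpatient with no ± 2-day window. SAP 4 plans at least 30 robust completers among the 100. If those 30 have no last-dose offset, the average excess is at most 0.70 × 1.25% = 0.87%, which is the 0.809 case. Some of these visits may be outpatient with approval, so this is a guide only.

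**The case against.** The strongest reply is that the protocol already fixes the draw. Day 225 ± 2 appears in the section 3.7 text, in the PK footnotes and in both visit tables, and Table 5.2-1 copies it. Section 3.7 states the last-dose rule in the same paragraph. A sample meeting both rules is always mapped and always within 2 days of its postdose target. This stands, and it confines the point to off-schedule doses or visits. Protocol 3.7.7 also schedules only one end-of-interval draw per subject (the draw before it is Day 218), so the only question is whether that one sample counts.

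A reader might infer more. The documents do not support these readings:

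- **Substantial loss of data.** If only the last-dose rule applied and offsets were uniform, 6/25 = 24% of samples would be unmapped; dropping them would leave 38 per group and power of 0.71. That sets aside the Day 225 ± 2 rule, gives robust subjects dose scatter that their visit table does not show, and assumes an exclusion that no visible text states.
- **Accumulating drift.** Letting each interval slip by 2 days would put correctly timed samples on Days 217-233 (2M LAI) or 209-241 (400 mg). The target-date rule does not allow it.
- **Off-schedule doses made acceptable by SAP 7.3.** Compliance there means an injection "in the minimum interval of 26 days or 960 mg aripiprazole 2M LAI injection at least 54 days after the prior injection", a minimum only. But that is a descriptive summary. It selects no PK sample and changes no visit window.
- **No rule for out-of-window samples.** None is visible, but parts of the SAP are blacked out, including text at the end of the PK section, so a missing rule cannot be asserted.

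The 8-15% shifts may also be high. Protocol 1.3 reports median times to peak of 25.1 and 41.0 days and a secondary peak for the LAI, so full terminal decline by days 52-60 is not established. At the 28-day absorption half-life given there for the 400 mg product, 4 days is 2^(∓4/28) = 0.906 and 1.104, about 9-10%.

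**Conclusion.** The mismatch is real: the window for a primary endpoint is counted from a different injection than the endpoint itself. It matters only when the last dose or the final visit is off schedule. In that case the table by itself can accept a sample up to 4 days from its postdose target, or leave a correctly timed one unmapped.

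The effect is small. Timing noise costs at most about 0.5 points of C56 power even if every last dose carries ± 2-day scatter, and less once the robust schedule is allowed for. Visit scatter and the slope near trough are assumptions, since the documents give neither. No bias between arms is shown and no loss of data is demonstrated. Severity is minor, and the case for changing the table is that it should agree with its own endpoint.

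**What to change.** - In Table 5.2-1, define the primary samples by elapsed days since the actual last injection, using the documents' own ± 2 days: C56 is the sample 54-58 days after the actual fourth 2M LAI injection, and C28 the sample 26-30 days after the actual eighth 400 mg injection.
- Add a sensitivity analysis that uses all determined values regardless of window.
- Reconcile the two statements of final-visit timing (days after the last dose, and Day 225 ± 2), and say whether both must hold. Which visit rule applies is for the sponsor to settle.

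The cost is one table row, one sentence on the sensitivity analysis and a clarification of the visit rule. Protocol 3.7.7 already requires the exact times of dosing and blood collection to be recorded, so no new data are needed.
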